4.1 Primary endpoint

4.1.1 Objectives:

The primary objective of this study will be to evaluate the safety and feasibility of time varying caloric vestibular stimulation (tvCVS), delivered with a solid-state TNM™ Device, in people with mild/moderate Parkinson's disease dementia (PDD).

4.1.2 Endpoint:

The primary endpoints of this study are the following:

- Safety will be evaluated by evaluating whether tvCVS is associated with a worsening of PD signs and symptoms according to The International Parkinson and Movement Disorder Society Unified Parkinson's Disease Rating Scale Total Score: composite score of Parts I, II and III.

Adverse events will also be monitored.

- Feasibility:
 - Retention rate or the percent of participants that complete assessments required for analysis of the secondary endpoint:
 - High retention: >90%
 - Moderate retention: 60-90 %
 - Low retention:< 60 %
 - Treatment adherence rate during the 12-week treatment period:
 - High adherence: >84%
 - Moderate adherence: 55-84 %
 - Low adherence: < 55 %

4.2 Secondary endpoints

4.2.1 Objectives:

The secondary objective of this trial is to assess the effects of tvCVS on cognition in people with mild/moderate PDD.

4.2.2 Endpoints:

The secondary endpoint will be the change in the Montreal Cognitive Assessment (MoCA) between the baseline and end of treatment visit (Day 84) after 12 weeks of treatment. 3 different versions of the MoCA (8.1, 8.2, and 8.3) will be used to avoid learning effects, and the ordering of the version for a given participant will be randomized. The MoCA is a rapid screening instrument for detecting cognitive dysfunction and dementia in patients with neurologic disorders including PD.

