Screening steps: The screening activities should be performed per the schedule of events (SOE) noted in the appendix, and the rater assessments in the order noted below. If at any time study staff recognizes that the recruit does not meet the inclusion and exclusion criteria for the study, they will inform the individual being screened and will note the reason

SHARPEN, V3.0 -- CONFIDENTIAL

Clinician version – not for patient use

for screen failure in the study documentation.

- Mini-Mental State Examination (MMSE)
- Intake of medical history and concomitant medications
- Ear exam- *The purpose of the exam (by otoscope) is to ensure that there are no contraindications to placing the device earpieces into the ear canals such as signs of inflammation, drainage, perforation of tympanic membrane, or excessive cerumen build up. Additionally, visual inspection for obvious structural abnormalities of the ear structure and ear canal should be included. As delegated by the PI, medical professionals who hold licenses/credentials, and have appropriate training and experience may conduct the ear exam.*
- Columbia Suicide Severity Rating Scale (C-SSRS) - questionnaire regarding suicidal thoughts
- Urinalysis- this does not need to be performed at the screening visit if there are normal range values documented in the medical record within 6 months of the screening visit.
- Blood draw for screening labs - B12, TSH, CMP, and CBC w/differential may be required. These labs do not need to be performed at the screening visit if there are normal range values documented in the medical record within 6 months of the screening visit.
- Review of Inclusion and Exclusion Criteria
- Review of the general study schedule and timeline, with assessment scheduling.

Baseline Visit- day 0: The baseline activities should be performed per the SOE in the appendix maximizing the time between administration of the MoCA (to be completed first) and the Customized Cognitive Battery (alternate versions to be used at all study visits). Assessments followed by (SP) should be completed by the Study Partner only.

- Confirmation of timing of last dopamine replacement therapy (DRT) dose
- Montreal Cognitive Assessment (MoCA) v8.1 (on-state) ⁺*Of note, if the participant has completed v8.1 in their standard clinical course within 5 weeks of this administration, they should perform v8.2 at this visit, then v8.1 at the interim visit.*

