- NAB Visual Discrimination
- Oral SDMT
- HVLT-R (Trial 4 and Recognition)
- D-KEFS Category Fluency (skip Condition 1-Letter Fluency for this study)
- D-KEFS Fluency Switching

If the CCB could not be performed at Day 0 or Day 3, then no further attempts should occur and the participant is not considered as part of the sub-study.

Virtual visits will be performed, as necessary, using the site's standard of care telemedicine platform.

Early Treatment Period Visit 2 - day 6 (+/- 3 days) – as needed: *This in-clinic visit may be completed virtually at the participant and study partner's request. This visit only needs to be completed if the study participant and study partner required retraining on use of the study device at the Early Treatment Period Visit 1 - day 3.* The participant (with the assistance of the study partner as appropriate) should complete a treatment administration at the study site to demonstrate to study staff an understanding of how to use the study Device. If participants and their study partner meet the criteria specified in the Treatment Administration Verification Form, the participant will then take the study Device home, treat once more for the day, and commence again with twice daily treatments. If participants and their care partners do not meet the criteria specified in the Treatment Administration Verification Form, the participant will **be withdrawn from the study.**

Phone contacts: (Days 14, 28, +/- 3 day)

During phone calls scheduled every 2 weeks, study staff will review concomitant medications, potential adverse events, potential issues impacting Device treatment adherence and any other issues with the study participant (and study partner, as appropriate). Care should be taken to not over-engage or impact feasibility of protocol adherence with reminders or contact outside of the protocol-defined visits/calls.

Interim treatment Visit: (Day 42 +/- 5 days)

The visit activities should be performed per the SOE. Assessments followed by (SP) should be completed by the study care partner only.

- Confirmation of timing of last DRT dose

SHARPEN, V3.0 -- CONFIDENTIAL

Clinician version – not for patient use

- MoCA v8.2 (on-state)

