- MDS-UPDRS III - clinician-scored motor exam *+Of note, the collection of MDS-UPDRS Part III data should occur in the on-state. The timing of the administration of the MDS-UPDRS Part III from dose should be recorded and kept consistent at each administration of the assessment for that participant.*
- MDS- UPDRS I - patient and caregiver in equal proportion
- MDS-UPDRS II - patient and caregiver in equal proportion
- NPI-Q *(SP)*
- ZBI *(SP)*
- S&E
- Ear Exam
- Concomitant medication and adverse event review

Phone contacts: (Days 56, and 70 +/- 3 day)

The study staff should continue phone calls scheduled every 2 weeks to review concomitant medications, potential adverse events, potential issues impacting Device treatment adherence and any other issues with the study participant (and study partner, as appropriate).

End of Treatment Visit or Early Termination Visit: (Day 84 +/- 5 days)

The visit activities should be performed per the SOE in the appendix maximizing the time between administration of the MoCA (to be completed first) and the Customized Cognitive Battery. Assessments followed by (SP) should be completed by the study partner only.

- Confirmation of timing of last DRT dose
- MoCA v8.3 (on-state)
- MDS-UPDRS III - clinician-scored motor exam *+Of note, the collection of MDS-UPDRS Part III data should occur in the on-state. The timing of the administration of the MDS-UPDRS Part III from dose should be recorded and kept consistent at each administration of the assessment for that participant.*
- MDS- UPDRS I - patient and caregiver in equal proportion
- MDS-UPDRS II - patient and caregiver in equal proportion
- PGI-S/PGI-I
- NPI-Q *(SP)*
- ZBI *(SP)*
- S&E
- Device Useability Questionnaires (Study Participant and Study Partner)
- Ear Exam
- Customized Cognitive Battery (Form 2) *-optional sub study. The best practice is to collect this data in the way it was collected at baseline. For instance, if a participant completed the CCB at the Baseline Visit – day 0 they should complete the CCB at the end of treatment visit. If the first CCB was collected at the Early Treatment Period Visit 1 - day 3, the best practice would be to have them return for a separate visit within 5 days of the end of treatment visit, while continuing to treat with the study device. The CCB must be collected at a single study visit. Data collection of the CCB should not occur in Off-state. Tests should be administered in the following order:*

- HVLT-R (Trials 1-3)

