2. STUDY DESIGN

This is a single arm study designed to evaluate the safety and feasibility of twice daily time-varying caloric vestibular stimulation (tvCVS) treatments using a solid-state Device developed by Scion NeuroStim, Inc. (SNS), also known as ThermoNeuroModulation (TNMTM), in patients with mild/moderate Parkinson's disease dementia (PDD) and to collect initial evidence to support proof of concept for the treatment of mild/moderate dementia in Parkinson's disease (PD). Participants will self-administer (with assistance, if necessary) ~19-minute *BID* treatments of tvCVS treatment over a period of 12 weeks (84 days). The study will be conducted at 2 centers located in the United States. This single-arm exploratory clinical trial will continue with competitive enrollment until 12 participants receive at least 1 treatment with the study Device at which point competitive enrollment will be closed.

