6.6.2 SECONDARY ENDPOINTS

The secondary endpoint will be the change at the end of treatment or early termination visit from baseline in the Montreal Cognitive Assessment (MoCA) score.

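### Protocol 4.2.2 randomises the MoCA version order but 5.1.1 fixes it by visit; if 5.1.1 is followed, any version difference enters the MoCA change in full and cannot be estimated from the trial data

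*Protocol*

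**What the plan says.** Protocol 4.2.2 makes the MoCA change from baseline to Day 84 the only secondary endpoint. It provides for three versions, to avoid learning effects, and states that "the ordering of the version for a given participant will be randomized".

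Protocol 5.1.1 names a version at every visit:
- Baseline: "Montreal Cognitive Assessment (MoCA) v8.1 (on-state".
- Day 42: "MoCA v8.2 (on-state".
- Under the heading "End of Treatment Visit or Early Termination Visit": "MoCA v8.3 (on-state".

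There is one exception. Of a participant who took v8.1 in routine care within the previous 5 weeks, 5.1.1 says "they should perform v8.2 at this visit, then v8.1 at the interim visit". That is a set rule, not a random one, and it leaves v8.3 at the final visit.

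The Schedule of Events (Protocol Appendix 1.0) says only that versions alternate. SAP 6.6.2 reads "The secondary endpoint will be the change at the end of treatment or early termination visit from baseline" and does not mention version. The default in SAP 6.5, a paired Wilcoxon signed-rank test, has no version term.

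**The concern.** Sites work from the visit lists. If they follow 5.1.1, the randomisation in 4.2.2 never happens, and a report that repeats 4.2.2 would describe something that was not done. If they follow 4.2.2, they depart from 5.1.1 at most visits.

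The choice affects the endpoint. SAP 2 describes a single-arm study meant "to collect initial evidence to support proof of concept". With no control arm, a difference in difficulty between forms is not cancelled by a comparison group. Only the version order can keep it out of the mean change.

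**Working it through.** The plan has no figure of its own on this point. The check is whether the change over time can be separated from version under each text, and how large the version contribution is.

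**Inputs.** Planned n = 12 treated (Protocol 10.1, SAP 4). The go/no-go minimum is 75% completing, and 0.75 × 12 = 9. Let d be the score on v8.3 minus the score on v8.1 for the same person with unchanged cognition. The documents do not give d. For the calculations v8.2 is assumed to lie halfway, so the version effects are 0, d/2 and d.

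**Separability.** Write change = time effect + effect of the final version − effect of the baseline version. The unknowns are three: time, v8.2 and v8.3, with v8.1 as reference.
- 5.1.1 with no swaps: all 12 design rows are identical, so the rank is 1 of 3 and the time effect is not estimable.
- 5.1.1 with 1, 3, 6 or 11 swaps: rank 2 of 3, still not estimable, because v8.3 is never a baseline form.
- Adding Day 42, with participant, visit and version effects: rank 14 of 16 with no swaps and 15 of 16 with three. The Day 84 effect is not estimable in either case.
- Six orders used twice each: rank 3 of 3 (16 of 16 with Day 42), estimable.

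**Bias under 5.1.1.** A standard participant contributes d, and a swapped one d − d/2 = d/2. With k swaps in 12, the mean bias is d(1 − k/24):
- k = 0: d
- k = 1: 0.96d
- k = 3: 0.875d

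**Bias under 4.2.2, simple randomisation.** Final minus baseline version effect over the six equally likely orders is d, d/2, d/2, −d/2, −d/2 and −d. The mean is 0. The variance is (1 + 4 × 0.25 + 1)/6 × d² = 0.5d².
- n = 12: SD = √(0.5/12) d = 0.20d
- n = 9: SD = √(0.5/9) d = 0.24d
- Chance of a bias of at least 0.5d in either direction (exact convolution): 1.7% at n = 12 and 4.3% at n = 9

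If v8.2 equals v8.1 or v8.3 instead, the variance is 0.667d² and the SDs are 0.24d and 0.27d.

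**Bias with a balanced list (two of each order).** It is exactly 0 if the 12 treated participants use those 12 entries and all complete. Two things can break the balance.
- *Dropout.* With 3 of 12 lost at random, the SD is √[(6/11)/9 × (1 − 9/12)] d = 0.12d. The worst case is 2.5d/9 = 0.28d.
- *Late screen failure.* In 5.1.1 the MoCA comes first at baseline, and the later device comfort check can still cause a screen failure. If k such failures, at random, use up entries that are replaced from a second block of six, the SD is √[k(6/11)(1 − k/12) + k(3/5)(1 − k/6)] d/12. That is about 0.08d, 0.11d and 0.12d for k = 1, 2 and 3, even if all 12 treated participants complete.

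**The case against.** The strongest case against is about weight. No document gives a difference between the versions, so the harm may be zero. The trial has no control arm, and time, practice and expectation stay confounded with treatment under either text. Randomising the order removes one possible bias from a change that still cannot be attributed to the device. External data on form equivalence could also bound d, although the trial's own data cannot. All of this stands, and it limits how much the point matters.

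It can also be said that 5.1.1 is the intended text. It is the more specific one, its swap rule presupposes a default that starts with v8.1, and it fixes the forms of the optional cognitive battery by visit as well. That is plausible, but the documents do not settle it. If it is right, the sentence in 4.2.2 is wrong and has to go.

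A reader might go further and infer that the trial risks a false-positive MoCA finding at some stated rate. The documents do not support that. Any rate would rest on an assumed d and an assumed SD, and the SAP sets no alpha or success rule for the MoCA. Nor is the go/no-go decision undermined: it uses serious adverse device effects and completion of the end-of-treatment assessment, not the score. Retention likewise counts completion, whichever version is given.

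**Conclusion.** The contradiction is certain and is in current text; it is not an amendment-log difference. One of the two sections must be breached as written.

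The consequence is conditional. Under 5.1.1 the bias in the mean MoCA change equals the difference between v8.3 and the baseline version, in either direction, and the trial data cannot estimate it. Under 4.2.2 it is zero in expectation but not in each realised sample. The multiples of d assume that v8.2 lies halfway unless stated otherwise. The finding that time and version cannot be separated under 5.1.1 does not depend on that assumption.

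The documents do not show that the versions differ, that the MoCA result will be biased, or which section was intended. The point concerns a secondary, proof-of-concept endpoint. It should be fixed because the repair is cheap.

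**What to change.** Reconcile the two sections. The preferred route, because it removes this bias in expectation, is to keep 4.2.2 and change 5.1.1:
- Replace the version labels with the participant's assigned order, taken from one central list in balanced blocks over the six orders.
- Include at least one spare block. Return to the list the order of anyone who takes the baseline MoCA but screen-fails before a first treatment, so that the 12 treated participants stay as balanced as possible.
- Give a participant who had v8.1 in the past 5 weeks the next unused order that does not start with v8.1.
- Use the third version in the assigned order at the end of treatment or early termination visit, whether or not Day 42 took place.
- Record the version given at each visit and list it with the MoCA results.

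The cost is a central list shared by about two sites, with no extra visits or tests. If the versions differ, the SD of change also rises, by √(SD² + 0.5d²)/SD − 1. For an assumed SD of 2 to 3 points, that is about 1–2% at d = 0.5, 3–6% at d = 1.0 and 6–13% at d = 1.5.

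If the fixed order is intended, delete the randomisation clause in 4.2.2 and state in SAP 6.6.2 that version and visit cannot be separated. That costs one deletion and one sentence, and leaves the limitation in place.

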4.3 Exploratory Endpoints

4.3.1 Objectives:

This study will also seek to further assess the effects of tvCVS on cognition and other symptoms in people with mild/moderate PDD.

4.3.2 Endpoints:

The exploratory endpoints will evaluate changes in the following between the baseline and end of treatment visit (Day 84) after 12 weeks of treatment, unless otherwise noted:

- The Zarit Burden Interview of Caregivers (ZBI) – a measure of caregiving burden completed by caregivers
- The Patient Global Impression of Improvement (PGI-I) - a patient reported outcome assessment for how much the patient's illness has improved or worsened relative to a baseline state at the beginning of the intervention. * *This version will require input from the study partner and will provide a single consensus score between the study participant and study partner.*
- The Neuropsychiatric Inventory - Questionnaire (NPI-Q) – a brief questionnaire completed by caregivers to evaluate behavioral disturbances in dementia patients – *to be completed by the study partner*
- The Modified Schwab and England Activities of Daily Living Scale (S & E)⁴⁵ - clinical outcome assessment of an individual's ability to function in activities of daily living

Treatment adherence and TNM™ Device usability/satisfaction will also be assessed.

Optional Sub-study:

For those that consent to this optional sub-study: A customized cognitive battery (CCB) which will assess the following functions (alternate versions to be used at each study visit):

- Memory
 - Hopkins Verbal Learning Test-Revised (total learning)
 - Hopkins Verbal Learning Test-Revised (delayed recall)
 - Hopkins Verbal Learning Test-Revised (recognition discrimination)
- Visuospatial
 - Neuropsychological Assessment Battery - Visual Discrimination
- Language
 - Delis-Kaplan Executive Function System - Semantic Fluency
- Attention
 - Neuropsychological Assessment Battery – Digits Forward
 - Hopkins Verbal Learning Test-Revised (Trial 1)
- Processing speed
 - Oral Symbol Digit Modality
- Executive Function

Clinician version – not for patient use

- Delis-Kaplan Executive Function System - Semantic Fluency Switching
- Neuropsychological Assessment Battery – Digits Backward

5 Study design:

5.1 Study Schedule and Activities

The phases and activities of the study are listed below, and sites are encouraged to break up the visit into multiple parts, as necessary, to reduce participant and study partner burden.

5.1.1 Study Activities

Pre-screening procedures: Sites will recruit potential participants from their practice/service or the general public as long as inclusion/exclusion criteria can be verified. The use of advertisements may be used at the site's discretion. During the pre-screening period, the study should be described, preliminary questions answered, and review of potential participant's medical records can occur, however, no protocol-specific activities should occur until after informed consent is obtained and documented.

Study screening procedures (Day-21 to -1):

Informed Consent

Participants will be shown an example of the Study Device as part of the informed consent process. Potential participants should be given a private space to review the Informed Consent Form (ICF) and an ample opportunity to have all questions answered. Capacity to provide consent must be assessed and documented by a clinician with experience working with Parkinson's Disease patients, and determination should be made if a Legally Authorized Representative (LAR) is required. Potential participants and LARs should be given a private space to review the ICFs and receive ample opportunity to have all questions answered. As this study population may have diminished capacity, open ended questions to confirm understanding should be used. The ICF should be signed and dated by both the study participant (or the LAR as necessary) and the authorized study staff performing the informed consent process. A signed and dated copy of the ICF should be provided to the participant (or LAR) prior to any study related activities being conducted.

Additionally, the protocol-required study partner will also be provided an ICF to review and discuss. The purpose of the informed consent for the study partner is to ensure that they understand and agree that they should attend all visits, are required to answer specific questions by the study staff related to the participant's overall health and activities of daily living, as well as mechanically assist the participant with the administration of the device (as necessary). The study partner should be afforded the same informed consent process stipulations as the participant, including that the informed consent be signed and dated by both the study partner and the authorized research study staff performing the informed consent process, and provided a sign and dated copy.

Screening steps: The screening activities should be performed per the schedule of events (SOE) noted in the appendix, and the rater assessments in the order noted below. If at any time study staff recognizes that the recruit does not meet the inclusion and exclusion criteria for the study, they will inform the individual being screened and will note the reason

SHARPEN, V3.0 -- CONFIDENTIAL

Clinician version – not for patient use

for screen failure in the study documentation.

- Mini-Mental State Examination (MMSE)
- Intake of medical history and concomitant medications
- Ear exam- *The purpose of the exam (by otoscope) is to ensure that there are no contraindications to placing the device earpieces into the ear canals such as signs of inflammation, drainage, perforation of tympanic membrane, or excessive cerumen build up. Additionally, visual inspection for obvious structural abnormalities of the ear structure and ear canal should be included. As delegated by the PI, medical professionals who hold licenses/credentials, and have appropriate training and experience may conduct the ear exam.*
- Columbia Suicide Severity Rating Scale (C-SSRS) - questionnaire regarding suicidal thoughts
- Urinalysis- this does not need to be performed at the screening visit if there are normal range values documented in the medical record within 6 months of the screening visit.
- Blood draw for screening labs - B12, TSH, CMP, and CBC w/differential may be required. These labs do not need to be performed at the screening visit if there are normal range values documented in the medical record within 6 months of the screening visit.
- Review of Inclusion and Exclusion Criteria
- Review of the general study schedule and timeline, with assessment scheduling.

Baseline Visit- day 0: The baseline activities should be performed per the SOE in the appendix maximizing the time between administration of the MoCA (to be completed first) and the Customized Cognitive Battery (alternate versions to be used at all study visits). Assessments followed by (SP) should be completed by the Study Partner only.

- Confirmation of timing of last dopamine replacement therapy (DRT) dose
- Montreal Cognitive Assessment (MoCA) v8.1 (on-state) ⁺*Of note, if the participant has completed v8.1 in their standard clinical course within 5 weeks of this administration, they should perform v8.2 at this visit, then v8.1 at the interim visit.*
- MDS-UPDRS III - clinician-scored motor exam ⁺*Of note, the collection of MDS-UPDRS Part III data should occur in the on-state. The timing of the administration of the MDS-UPDRS Part III from dose should be recorded and kept consistent at each administration of the assessment for that participant.*
- MDS- UPDRS I –patient and caregiver in equal proportion
- MDS-UPDRS II– patient and caregiver in equal proportion
- PGI-S – should be completed with input from study participant and study partner in equal proportion
- PGI-S response documentation: study staff should ask the study participant and study partner to give at least three reasons for their score and answers will be recorded and will be provided to the study participant and study partner at future administrations of the PGI-I.
- S&E
- NPI-Q *(SP)*
- ZBI *(SP)*
- Ear Exam
- Concomitant medication and adverse event review

SHARPEN, V3.0 -- CONFIDENTIAL

Clinician version – not for patient use

Customized Cognitive Battery (CCB) Form 1 — *optional substudy* *** *The best practice is to collect this data at the baseline visit, however, if participant is unable to complete the CCB at the baseline visit, he/she may complete the CCB at the Early Treatment Period Visit 1 - day 3 visit as an alternative. The CCB must be collected at a single study visit and at the study center. Data collection of the CCB should not occur in Off-state. Tests should be administered in the following order:*

- HVLT-R (Trials 1-3)
- NAB Digits Forward
- NAB Digits Backward
- NAB Visual Discrimination
- Oral SDMT
- HVLT-R (Trial 4 and Recognition)
- D-KEFS Category Fluency (skip Condition 1-Letter Fluency for this study)
- D-KEFS Fluency Switching
- Review of inclusion/exclusion criteria
- Device dispensation and training
- First device administration with confirmation of understanding

The participant should be fitted, and the device adjusted as necessary with the ear pad selection documented. Participants should confirm that they find wearing the unpowered device to be comfortable enough to proceed with the study treatment prior to device dispensation. If they do not, the reason for screen failure should be noted in the study documentation.

Device dispensation will occur only after all scheduled assessments and activities have been completed. The participant and study partner will be trained on how to use and care for the Device. The participant (with the assistance of the study partner as appropriate) should complete the first treatment administration at the study site to demonstrate to study staff an understanding of how to set-up, use, and clean the study Device. The participant will then take the study Device home, treat once more for the day, and continue with twice daily treatments for the duration of the treatment period.

Treatment Period: The 12 weeks (~84 days) following the pre-treatment baseline period constitute the treatment period. Participants will self-administer treatments twice daily with at least an hour in between treatment sessions, for the full treatment period up until the scheduled end of treatment visit. Treatment adherence will be recorded by the Device.

Phone contact (Day 1, +/- 1 day)

The first day (Day 1) after Device allocation, the study staff should contact the participant/study partner to confirm that treatments have been administered, that there are no questions or concerns about the Device and to review concomitant medications and potential adverse events.

Early Treatment Period Visit 1 - day 3 (+/- 3 days): *This in-clinic visit may be completed virtually at the participant and study partner's request if the customized cognitive battery does not need to be collected.* The participant and study partner should return to the clinic with the study device. The study participant (with the assistance of the study partner as

SHARPEN, V3.0 -- CONFIDENTIAL

Clinician version – not for patient use

appropriate) should complete a treatment administration at the study site to demonstrate to study staff an understanding of how to use the study Device. If participants and their study partners do not meet the criteria specified in the Treatment Administration Verification Form, the participant and study partner will be re-trained on how to use and care for the Device. The participant will then take the study Device home, treat once more for the day, and continue with twice daily treatments for the duration of the treatment period.

CCB (if not collected at the Baseline day 0 visit)- *Data collection of the CCB should not occur in Off-state. Tests should be administered in the following order:*

- HVLT-R (Trials 1-3)
- NAB Digits Forward
- NAB Digits Backward
- NAB Visual Discrimination
- Oral SDMT
- HVLT-R (Trial 4 and Recognition)
- D-KEFS Category Fluency (skip Condition 1-Letter Fluency for this study)
- D-KEFS Fluency Switching

If the CCB could not be performed at Day 0 or Day 3, then no further attempts should occur and the participant is not considered as part of the sub-study.

Virtual visits will be performed, as necessary, using the site's standard of care telemedicine platform.

Early Treatment Period Visit 2 - day 6 (+/- 3 days) – as needed: *This in-clinic visit may be completed virtually at the participant and study partner's request. This visit only needs to be completed if the study participant and study partner required retraining on use of the study device at the Early Treatment Period Visit 1 - day 3.* The participant (with the assistance of the study partner as appropriate) should complete a treatment administration at the study site to demonstrate to study staff an understanding of how to use the study Device. If participants and their study partner meet the criteria specified in the Treatment Administration Verification Form, the participant will then take the study Device home, treat once more for the day, and commence again with twice daily treatments. If participants and their care partners do not meet the criteria specified in the Treatment Administration Verification Form, the participant will **be withdrawn from the study.**

Phone contacts: (Days 14, 28, +/- 3 day)

During phone calls scheduled every 2 weeks, study staff will review concomitant medications, potential adverse events, potential issues impacting Device treatment adherence and any other issues with the study participant (and study partner, as appropriate). Care should be taken to not over-engage or impact feasibility of protocol adherence with reminders or contact outside of the protocol-defined visits/calls.

Interim treatment Visit: (Day 42 +/- 5 days)

The visit activities should be performed per the SOE. Assessments followed by (SP) should be completed by the study care partner only.

- Confirmation of timing of last DRT dose

SHARPEN, V3.0 -- CONFIDENTIAL

Clinician version – not for patient use

- MoCA v8.2 (on-state)
- MDS-UPDRS III - clinician-scored motor exam *+Of note, the collection of MDS-UPDRS Part III data should occur in the on-state. The timing of the administration of the MDS-UPDRS Part III from dose should be recorded and kept consistent at each administration of the assessment for that participant.*
- MDS- UPDRS I - patient and caregiver in equal proportion
- MDS-UPDRS II - patient and caregiver in equal proportion
- NPI-Q *(SP)*
- ZBI *(SP)*
- S&E
- Ear Exam
- Concomitant medication and adverse event review

Phone contacts: (Days 56, and 70 +/- 3 day)

The study staff should continue phone calls scheduled every 2 weeks to review concomitant medications, potential adverse events, potential issues impacting Device treatment adherence and any other issues with the study participant (and study partner, as appropriate).

End of Treatment Visit or Early Termination Visit: (Day 84 +/- 5 days)

The visit activities should be performed per the SOE in the appendix maximizing the time between administration of the MoCA (to be completed first) and the Customized Cognitive Battery. Assessments followed by (SP) should be completed by the study partner only.

- Confirmation of timing of last DRT dose
- MoCA v8.3 (on-state)
- MDS-UPDRS III - clinician-scored motor exam *+Of note, the collection of MDS-UPDRS Part III data should occur in the on-state. The timing of the administration of the MDS-UPDRS Part III from dose should be recorded and kept consistent at each administration of the assessment for that participant.*
- MDS- UPDRS I - patient and caregiver in equal proportion
- MDS-UPDRS II - patient and caregiver in equal proportion
- PGI-S/PGI-I
- NPI-Q *(SP)*
- ZBI *(SP)*
- S&E
- Device Useability Questionnaires (Study Participant and Study Partner)
- Ear Exam
- Customized Cognitive Battery (Form 2) *-optional sub study. The best practice is to collect this data in the way it was collected at baseline. For instance, if a participant completed the CCB at the Baseline Visit – day 0 they should complete the CCB at the end of treatment visit. If the first CCB was collected at the Early Treatment Period Visit 1 - day 3, the best practice would be to have them return for a separate visit within 5 days of the end of treatment visit, while continuing to treat with the study device. The CCB must be collected at a single study visit. Data collection of the CCB should not occur in Off-state. Tests should be administered in the following order:*

- HVLT-R (Trials 1-3)

- NAB Digits Forward
- NAB Digits Backward
- NAB Visual Discrimination
- Oral SDMT
- HVLIT-R (Trial 4 and Recognition)
- D-KEFS Category Fluency (skip Condition 1-Letter Fluency for this study)
- D-KEFS Fluency Switching
- Concomitant medication and adverse event review
- Device Return - used Devices will be promptly shipped back to the distributor using the Device Return form. ** Device return should occur after completion of the Customized Cognitive Battery, if the participant consents to this sub-study and cannot complete the CCB on the same day.

